7.2. Participant Discontinuation/Withdrawal From the Study

A participant may withdraw from the study at any time at their own request. Reasons for discontinuation from the study include the following:

- Refused further follow-up;
- Lost to follow-up;
- Death;
- Study terminated by sponsor.

At the time of discontinuing from the study, if possible, an discontinuation visit should be conducted. See the [SoA](#) for assessments to be collected at the time of study discontinuation and follow-up and for any further evaluations that need to be completed.

The discontinuation visit applies only to participants who are enrolled/randomized and then are prematurely withdrawn from the study. Participants should be questioned regarding their reason for withdrawal.

If a participant withdraws from the study, they may request destruction of any remaining samples taken and not tested, and the investigator must document any such requests in the site study records and notify the sponsor accordingly.

If the participant withdraws from the study and also withdraws consent (see [Section 7.2.1](#)) for disclosure of future information, no further evaluations will be performed and no additional data will be collected. The sponsor may retain and continue to use any data collected before such withdrawal of consent.

7.2.1. Withdrawal of Consent

Participants who request to discontinue receipt of study intervention will remain in the study and must continue to be followed for protocol-specified follow-up procedures. The only exception to this is when a participant specifically withdraws consent for any further contact with them or persons previously authorized by the participant to provide this information. Participants should notify the investigator in writing of the decision to withdraw consent from future follow-up, whenever possible. The withdrawal of consent should be explained in detail in the medical records by the investigator, as to whether the withdrawal is only from further receipt of study intervention or also from study procedures and/or posttreatment study follow-up, and entered on the appropriate CRF page. In the event that vital status (whether the participant is alive or dead) is being measured, publicly available information should be used to determine vital status only as appropriately directed in accordance with local law.

7.3. Lost to Follow-Up

A participant will be considered lost to follow-up if the participant repeatedly fails to return for scheduled visits and is unable to be contacted by the study site.

The following actions must be taken if a participant fails to return to the clinic for a required study visit:

- The site must attempt to contact the participant and reschedule the missed visit as soon as possible. Counsel the participant on the importance of maintaining the assigned visit schedule, and ascertain whether the participant wishes to and/or should continue in the study;
- Before a participant is deemed lost to follow-up, the investigator or designee must make every effort to regain contact with the participant (where possible, 3 telephone calls and, if necessary, a certified letter to the participant's last known mailing address or local equivalent methods). These contact attempts should be documented in the participant's medical record;
- Should the participant continue to be unreachable, the participant will be considered to have withdrawn from the study.

8. STUDY ASSESSMENTS AND PROCEDURES

8.1. Administrative and Baseline Procedures

The investigator (or an appropriate delegate at the investigator site) must obtain a signed and dated ICD before performing any study-specific procedures.

Study procedures and their timing are summarized in the [SoA](#). Protocol waivers or exemptions are not allowed.

Adherence to the study protocol, including those specified in the [SoA](#), is essential and required for study conduct.

All screening evaluations must be completed and reviewed to confirm that potential participants meet all eligibility criteria. The investigator will maintain a screening log to record details of all participants screened and to confirm eligibility or record reasons for screening failure, as applicable.

Every effort should be made to ensure that protocol-required tests and procedures are completed as described. However, it is anticipated that from time to time there may be circumstances outside the control of the investigator that make it unfeasible to perform the test. In these cases, the investigator must take all steps necessary to ensure the safety and well-being of the participant. When a protocol-required test cannot be performed, the investigator will document the reason for the missed test and any corrective and preventive actions that they have taken to ensure that required processes are adhered to as soon as possible. The study team must be informed of these incidents in a timely manner.

For samples being collected and shipped, detailed collection, processing, storage, and shipment instructions and contact information will be provided to the investigator site prior to initiation of the study.

The total blood sampling volume for individual participants in this study is approximately 150 mL. The actual collection times of blood sampling may change. Additional blood samples may be taken for safety assessments at times specified by Pfizer, provided the total volume taken during the study does not exceed 550 mL during any period of 60 consecutive days.

8.2. Efficacy Assessments

All efforts should be made to have EOT assessments performed in all participants. Participants with a successful overall outcome at EOT (prior to Day 42) must return for Day 42, Day 84, or other planned visits (eg, Day 126 and Day 168 for participants with IM) through EOT as specified in [SoA](#), even if they are no longer receiving study intervention. If administration of systemic antifungals as prophylaxis is anticipated following successful therapy, participants should remain on study intervention through the Day 42 visit, ie, do not start any non-study systemic antifungal medication until after the Day 42 visit.

Secondary prophylaxis for participants who are expected to receive additional courses of chemotherapeutic agents, undergo BMT/HSCT, or are anticipated to remain significantly immunosuppressed is acceptable after the Day 42 visit. Reasons for requiring secondary prophylaxis must be documented in the eCRF.

Participants withdrawn from study intervention or with an unsuccessful overall outcome at EOT and requiring alternative systemic antifungal therapy will not be asked to return for subsequent visits, but will be required to return for the FU visit which is planned on 4 weeks after the last dose of study intervention; however, the survival status at the time points as specified in [SoA](#) will be collected (confirmation by phone contact is acceptable and will be documented in the eCRF).

8.2.1. Clinical Signs and Symptoms of Invasive Fungal Infection

Assessment of signs and symptoms of IFD (refer to [Appendix 9, Section 10.9](#) for more detail) will be performed as specified in [SoA](#). All changes in clinical symptoms and physical findings related to IFD will be recorded on the eCRF.

8.2.2. Radiological Assessment of Invasive Fungal Infection

Initial local radiologic assessment of IFD by CT scan (or HRCT) or MRI may be used to determine participant eligibility at Screening. Baseline radiological assessments of IFD by CT should be performed once the participant has completed the informed consent. However, assessments performed up to 7 days after the first administration of study intervention may be used to confirm the diagnosis of IFD. Out-of-window assessments may be considered as baseline assessments upon sponsor's (or designee) prior approval.

Radiological assessments should be made by CT (or HRCT) or MRI and all radiological images and local reports pertaining to IFD will be based on investigators' discretion.

8.2.3. GM Antigen

GM antigen will be tested at Screening. If clinically indicated, can be tested during Day 1 to Day 7, for participants with IA only. Assessments performed up to 7 days after the first administration of study intervention may be used to confirm the diagnosis of IFD. All the "possible" IFD participants are required to conduct further diagnostic tests (at least GM antigen for participants with IA) to further confirm IFD as "probable" or "proven" within 7 days after the first administration of study intervention. Criteria regarding interpretation of GM test results refer to [Appendix 9, Section 10.9](#).

GM antigen result for eligibility at screening will be based on local lab test results.

In addition, samples obtained for GM antigen assay (or collected any time while participants with probable, proven or possible Aspergillus are still receiving study drug) will be shipped to a central laboratory. BAL for GM specimens may be processed locally, but an additional aliquot of BAL fluid will be collected for shipment to the central laboratory as well.

8.2.4. Bronchoscopic Assessment of Invasive Fungal Infection

If bronchoscopic assessments are clinically indicated, samples are to be obtained for the following tests: culture and histology/cytology. The culture and histology/cytology will be performed using local laboratories for eligibility assessment. If samples are obtained at baseline and up to Day 7, an additional sample will be stored for shipping to the central reference laboratory for mycological testing.

If BAL is sent for GM antigen testing, the results should be recorded in the eCRF. BAL for GM specimens will be processed locally.

8.2.5. Mycological Assessment of Invasive Fungal Infection

All mycological assessments will be based on results generated in the local laboratory to assess the participant's eligibility at screening and following mycological response. Pathogen isolates must be shipped to the central reference laboratory for confirmation of local mycological results.

Baseline mycological assessment (Screening through Day 7) of the participant's IFD status will be performed according to the microbiological manual or the best local practice using local laboratories, including obtaining suitable samples for fungal culture and isolation and/or biopsy/biological fluid samples from the infected site for histology/cytology. Day 42 and Day 84 assessments will be performed within ± 7 days, as well as Day 126 and Day 168 for IM participants. EOT assessments will be performed within ± 3 days.

Baseline and different (species level) pathogen isolates (defined as clinically significant isolates) will be stored and shipped to a central laboratory for isolation of fungal species and susceptibility testing.

If the identities of the pathogens differ between the central and local laboratories, the central laboratory results will take precedence over the local results for both eligibility and response evaluation purposes.

8.2.6. Neutropenic Status/Absolute Neutrophil Count

Neutropenic status will be recorded within 4 weeks prior to screening and up to the end of the study period. The presence or absence of neutropenia (defined as ANC $<0.5 \times 10^9/L$ [$<500/mm^3$]) and subsequent persistence (ongoing) or resolution (2 consecutive ANC values $> 0.5 \times 10^9/L$ on 2 separate days) will be reflected in the ANC values recorded in the eCRF. All ANCs performed (or calculated) at local laboratories during a neutropenic episode will be recorded in the eCRF along with the date drawn to include the values documenting the resolution. When differentials are not performed due to insufficient WBCs, the total WBCs will be recorded for that day in the eCRF.

8.2.7. Survival Status

Survival status will be recorded until the Follow-up visit and be evaluated through EOT in all participants, irrespective of when treatment was discontinued. Detailed requirement should be performed as specified in [Section 1.3 SoA](#).

If the participant has died, the date and cause of death along with the reporting of SAE details will be recorded in the eCRF.

8.2.8. Investigator's Assessment of Overall Response

The investigator's assessment of overall response will be recorded at Day 42, EOT and Day 84. For participants who had an overall response of failure at EOT (prior to Day 42 visit), assessment of response is not required on Day 42 and Day 84.

The investigator will be asked to provide his/her opinion of the participant's response as follows:

Clinical Response (all non-radiological clinical symptoms and physical findings):

- Resolution of all attributable clinical symptoms and physical findings
(ie, resolution of all clinical symptoms and physical findings of IFD present at baseline and/or resolution of those that appeared at a subsequent visit)
- Resolution of some attributable clinical symptoms and physical findings
(ie, resolution of some but not all clinical symptoms and/or physical findings of IFD present at baseline and/or of those that appeared at a subsequent visit)

- No resolution of any attributable clinical symptoms and physical findings and/or worsening

(ie, no resolution or worsening of any clinical symptoms and/or physical findings of IFD present at baseline and/or of those that appeared at a subsequent visit)

- Results not available/participant unevaluable

(ie, visit and/or assessment of clinical symptoms and physical findings of IFD was not performed at any time point [Day 42, EOT or Day 84])

- No attributable signs and symptoms at screening

(ie, no clinical symptoms or physical findings of IFD present at baseline)

Radiological Response:

- $\geq 90\%$ improvement
- $\geq 50\%$ to $< 90\%$ improvement
- $\geq 25\%$ to $< 50\%$ improvement
- $< 25\%$ improvement
- No signs on radiological images at screening (Proven IFD only)
- Results not available (ie, visit and/or radiological assessment was not performed at any time point [Day 42, EOT or Day 84])

Radiological assessments should be made by CT and all radiological images and local reports pertaining to IFD will be based on investigators' discretion.

Mycological Response:

- Eradication
(eradication of the original causative organism cultured or identified by histology/cytology at baseline)
- Presumed eradication
(missing documentation of the eradication of the original causative organism at baseline plus resolution of all or some clinical symptoms and physical findings of IFD present at baseline and/or of those that appeared at a subsequent visit)

- Persistence
(persistence of the original causative organism cultured or identified by histology/cytology at baseline or emergence of a new causative organism)
- Presumed persistence
(missing documentation of the persistence of the original causative organism at baseline plus no resolution or worsening of any clinical symptoms and physical findings of IFD present at baseline and/or of those that appeared at a subsequent visit)
- No mycological follow-up results available, for any reason
(no diagnostic test done at any time point of assessment [*Day 42, EOT, Day 84, Day 126, or Day 168*])
- No mycological evidence at screening (up to Day 7)
(any negative diagnostic test(s) obtained or not done at baseline [from screening up to Day 7 inclusive])

8.2.9. Definition of Response and Outcome

[Table 6](#) defines a successful overall outcome.

Participants with no host factors, except for those with a proven IFD, will have an overall response of indeterminate, regardless of their respective clinical, radiological, and mycological response.

Participants not available for assessment, who are considered to have had an overall response of failure, or required alternative systemic antifungal therapy prior to Day 42 and/or Day 84 and/or EOT will be considered as having had an overall response of failure at Day 42 and/or Day 84 and/or EOT.

In addition, death of a participant will always be considered an overall response of failure for subsequent assessments.

Table 6. Definition of Successful Overall Response

	Clinical Response	Radiological Response	Mycological Response
Success	
 Resolution of all attributable clinical symptoms and physical findings Resolution of some attributable clinical symptoms and/or physical findings 	
 90% improvement from screening ≥50% - <90% improvement from screening ≥25% - <50% improvement from screening¹ No signs on radiological images at screening (Proven IFD only) 	
 Eradication Presumed Eradication

Any one criterion from each response column is required to be considered to have an overall outcome of success.

- At Day 42 for participants with proven or probable IFD. At Day 84, however, this would be considered unsuccessful.

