- Intercurrent events and missing data: All data collected after use of the prohibited medications will be excluded. As the clinical response is one of the components toward the overall response, the results of clinical response will be summarized without regards to deaths. Missing data will be handled as described in Section 5.3. Any patient with a Not Done at a visit will be considered a missing and included as a failure. A participant with a NA assessment will be excluded from the denominators when calculating the percentages.

6.2.4.2. Mycological Response at EOT, Day 42 and Day 84

Outcome	Mycological assessment
Success	1. Eradication 2. Presumed Eradication
Failure	1. Persistence 2. Presumed Persistence
NA	1. No mycological evidence available at screening 2. No mycological follow-up results available

- Estimand strategy: While on-Treatment (Section 2.2.2).
- Analysis set: mITT and myITT-IA populations (Section 4).
- Analysis methodology: Number and percent of participants in the categories of Success and Failure will be summarized at Day 42, Day 84 and EOT. The 2-sided 95% CIs for crude success rate will be calculated based on a binomial distribution.
- Intercurrent events and missing data: All data collected after use of the prohibited medications will be excluded. As the mycological response is one of the components toward the overall response, the results of mycological response will be summarized without regards to deaths. Missing data will be handled as described in Section 5.3. A participant with a Not Done assessment at a visit will be considered missing and is included as a failure. A participant with a NA assessment will be excluded from the denominators when calculating the percentages.

6.2.4.3. Radiological Response at EOT, Day 42 and Day 84

Outcome	Radiological assessment
Success	1. $\geq 90\%$ improvement 2. $\geq 50\%$ to $< 90\%$ improvement 3. $\geq 25\%$ to $< 50\%$ improvement (for Day 42 only)
Failure	1. $< 25\%$ improvement at any time 2. Results not available
NA	No signs on radiological images at screening

An improvement between 25% and 50% from baseline is considered a radiological success for Day 42 and EOT (that is before Day 42). At least 50% improvement from baseline is considered a radiological success for visits on Day 42, Day 84 and EOT (that is after Day 42).

- Estimand strategy: While on-Treatment (Section 2.2.2).
- Analysis set: mITT and myITT-IA populations (Section 4).

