- Analysis methodology: Number and percent of participants in the categories of Success and Failure will be summarized at Day 42, Day 84 and EOT. The 2-sided 95% CIs for crude success rate will be calculated based on a binomial distribution.
- Intercurrent events and missing data: All data collected after use of the prohibited medications will be excluded. As the radiological response is one of the components toward the overall response, the results of radiological response will be summarized without regards to deaths. Missing data will be handled as described in Section 5.3. A participant with a Not Done assessment at a visit will be considered missing and is included as a failure. A participant with a NA assessment will be excluded from the denominators when calculating the percentages.

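### Once a proven-IFD participant is recorded as having no imaging signs at screening, no rule scores a new on-treatment lesion as radiological failure: the protocol counts success, the SAP drops the participant

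*Protocol*

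**What the plan says.** Protocol 8.2.8 offers the investigator six radiological options: four bands of percentage improvement, one for proven disease with no imaging signs at screening, and one for results not available. Table 6 in Protocol 8.2.9 then places "No signs on radiological images at screening (Proven IFD only" in the success list. The only visit restriction in the table is the footnote to the band from 25% to below 50%: "At Day 42 for participants with proven or probable IFD. At Day 84, however, this would be considered unsuccessful". The three columns combine by this rule: "Any one criterion from each response column is required to be considered to have an overall outcome of success".

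SAP 6.2.4.3 treats the category differently. It puts "No signs on radiological images at screening" in the NA row, and "A participant with a NA assessment will be excluded from the denominators when calculating the percentages". The failure row covers less than 25% "improvement at any time 2. Results not available", and an assessment marked Not Done also counts as failure. SAP 2.1 declares no modification of the protocol's analysis. SAP 6.2.3 takes overall response from the investigator's assessment and does not say how an NA radiological component enters it.

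The other two components allow for new disease. The worst clinical category includes "no resolution or worsening of any clinical symptoms and/or physical findings of IFD present at baseline and/or of those that appeared at a subsequent visit", and mycological persistence includes the emergence of a new causative organism (Protocol 8.2.8).

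**The concern.** The category describes the participant at entry but is used as an outcome at Day 42, EOT and Day 84. With no lesion at baseline, percentage improvement has no denominator, so this category is the natural one to record whatever the later scan shows. A participant whose imaging stays clear and one who develops lesions on treatment then get the same score.

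Two secondary results are at stake. One is the radiological success rate, which follows the SAP. The other is overall response, where Table 6 lets the baseline state satisfy the radiological column. The study is open-label (Protocol 6.3.1), and the images are left to the investigator's discretion (Protocol 8.2.2 and 8.2.8). The documents describe no independent review of response that would catch the problem.

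**Working it through.** The plan gives no figure on this point to reproduce. The check compares the rules and then bounds their effect.

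**1. Can the affected group exist?** Yes. Protocol Appendix 9 does not require clinical features for proven disease. Proven disease can rest on tissue damage seen microscopically, on culture from a clinically abnormal sterile site, or on blood culture.

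**2. How is a new lesion scored once the category is recorded?**

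| Rule | Scans stay clear | New lesion |
|---|---|---|
| Protocol Table 6 | success | success |
| SAP 6.2.4.3 | NA, excluded | NA, excluded |

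Neither rule separates the two columns.

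**3. Must another column catch it?** No. The clinical column is headed "Clinical Response (all non-radiological clinical symptoms and physical findings", so imaging alone does not enter it. Presumed eradication needs only missing mycological documentation plus resolution of some symptoms. A participant with a new lesion, one improved symptom and no repeat sampling therefore meets one success criterion in each column of Table 6.

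**4. Size.** The documents give neither the mITT size nor the number affected, so these are assumptions. Let n be the mITT size, k the number with no signs at screening, m the number of those k who develop new lesions, s the successes among the other n − k, and r = s/(n − k). The reference scoring is success if the scan is clear and failure if there is a new lesion.

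- Reference rate: (s + k − m)/n.
- Table 6 rate: (s + k)/n. Excess over the reference: m/n, at most k/n.
- SAP rate: s/(n − k) = r. Difference from the reference: r − [r(n − k) + k − m]/n = [m − (1 − r)k]/n.
- If all k progress (m = k), the SAP rate is too high by rk/n.
- If none progress (m = 0), the SAP rate is too low by (1 − r)k/n.

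With n = 40 and about 40% success among the others:

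| k | Counted as success | NA, excluded | Counted as failure |
|---|---|---|---|
| 1 | 17/40 = 42.5% | 16/39 = 41.0% | 16/40 = 40.0% |
| 3 | 18/40 = 45.0% | 15/37 = 40.5% | 15/40 = 37.5% |

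- Table 6, all progress: 42.5 − 40.0 = 2.5 points (k = 1); 45.0 − 37.5 = 7.5 points (k = 3).
- SAP, all progress: 41.0 − 40.0 = 1.0 point; 40.5 − 37.5 = 3.0 points, too high.
- SAP, all clear: 41.0 − 42.5 = −1.5 points; 40.5 − 45.0 = −4.5 points, too low.

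Over n = 30 to 66 and k = 1 to 5, the ceiling k/n runs from 1/66 = 1.5 points to 5/30 = 16.7 points. For scale, the exact 95% interval for 18/40 is 29.3% to 61.5%.

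**The case against.** The strongest reply is that the gap is narrow and the endpoints are lesser ones. Most routes to proven disease involve an imaging lesion or an abnormal site, so proven disease without imaging signs may be rare or absent. The primary endpoint (TEAEs) and the key secondary endpoint (Day 42 mortality) are untouched. The response rates are descriptive, with no hypothesis test. All of this stands, and it sets the severity.

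A reader might also infer three stronger things that the documents do not support.

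- *That the category is a radiological success at every later visit.* This is true of Table 6 only. In the SAP's radiological analysis it is NA and never a success.
- *That such a participant can never fail.* Results not available and Not Done are failures in the SAP. The options are not declared mutually exclusive, so an investigator might record less than 25% improvement for a new lesion, though no rule says to. Overall response can still fail through the clinical or mycological column, death, alternative systemic antifungal therapy or unavailability for assessment.
- *That the error can only favour the drug.* This holds for Table 6. The SAP's exclusion lowers the radiological rate when the scans stay clear.

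What remains is that no rule in either document turns a new lesion into a radiological failure once this category is recorded.

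**Conclusion.** The point holds in limited form. A baseline state stands in for a response, and the two documents score it in different ways, neither of which registers new radiological disease. The effect on overall response is at most k/n and reaches that only if every affected participant progresses yet passes the other two columns. The effect on the SAP's radiological rate is smaller and can go either way. The illustrative sizes rest on assumed values (n = 40, k = 1 to 3, a success rate of about 40% among the others); k could be zero. Severity is minor, but the row already needs reconciling because the protocol and SAP disagree on it.

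**What to change.** In Protocol 8.2.8, Table 6 and SAP 6.2.4.3, replace the single category with two:

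- no signs at screening and none at the assessed visit: success;
- no signs at screening and a new attributable lesion at the assessed visit: failure.

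Keep the limitation to proven disease in both documents, and apply the same scoring to the radiological rate and to the radiological column of overall response. This also removes the conflict between success and NA, and the open question of how NA enters overall response for these participants.

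The cost is a protocol clarification, one added CRF option and one added SAP table row. The scans are already scheduled at Day 42, Day 84 and EOT in the Schedule of Activities. Instructing investigators to record a new lesion as less than 25% improvement would avoid the CRF change, but the clear-scan case would still need one agreed score in both documents. The change affects scoring only, not treatment.

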6.2.3.1.1. Subgroup Analysis

If data permit, subgroup analyses will be performed for the overall response based on investigator's assessment at EOT based on mITT population for the aforementioned subgroups in Section 6.2.1.3, and the IFD location [lower respiratory tract disease (LRTD) only, LRTD plus Other Organ, Non LRTD only] .

6.2.3.2. The Crude Rates of Overall Response at Day 42 and Day 84

- Estimand strategy: While on-Treatment (Section 2.2.2).
- Analysis set: mITT and myITT-IA populations (Section 4).
- Analysis methodology: The crude rates of overall response based on investigator's assessment will be summarized by number and percentage of participants at Day 42 and Day 84, respectively. The 2-sided 95% CIs for crude rate will be calculated based on a binomial distribution.
- Intercurrent events and missing data: All data collected after use of the prohibited medications will be excluded. Missing data will be handled as described in Section 5.3. A participant that investigators' assessment indicated as Not Done at a visit will be considered as missing and will be included as a failure for the visit. Any death before Day 42 will be considered a failure by including in the death category for both timepoints. Any death occurring between Day 42 and Day 84 will be considered as a failure by including in the death category for Day 84.

6.2.4. Crude Success Rates of the Clinical, Mycological, Radiological Responses at EOT, Day 42 and Day 84

6.2.4.1. Clinical Response at EOT, Day 42 and Day 84

Outcome	Clinical response
Success	1. Resolution of all attributable clinical symptoms and physical findings 2. Resolution of some attributable clinical symptoms and physical findings
Failure	1. No resolution of any attributable clinical symptoms and physical findings and/or worsening 2. Results not available/Patient unevaluable
NA	No attributable signs and symptoms present at screening

- Estimand strategy: While on-Treatment (Section 2.2.2).

- Analysis set: mITT and myITT-IA populations (Section 4).
- Analysis methodology: Number and percent of participants in the categories of Success and Failure will be summarized at Day 42, Day 84 and EOT. The 2-sided 95% CIs for crude success rate will be calculated based on a binomial distribution.

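### A participant with no attributable symptoms at screening who stays symptom-free meets no clinical criterion in Table 6, so cannot count as an overall success

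*Protocol*

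**What the plan says.** Protocol 8.2.9, Table 6, defines overall success through a clinical, a radiological and a mycological column, and combines them with the sentence "Any one criterion from each response column is required to be considered to have an overall outcome of success". The clinical column has two entries: resolution of all attributable symptoms and findings, and "Resolution of some attributable clinical symptoms and/or physical findings". The radiological column has an entry for participants with nothing to see at baseline, "No signs on radiological images at screening (Proven IFD only", which is limited to proven disease as its bracket says.

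Protocol 8.2.8 gives the investigator five clinical categories. One is "No attributable signs and symptoms at screening". It is separate from the category for results that are not available, and it does not appear in Table 6. The same section lets resolution of all symptoms cover those present at baseline "and/or resolution of those that appeared at a subsequent visit". Presumed eradication applies when documentation is missing, "plus resolution of all or some clinical symptoms and physical findings of IFD present at baseline" or of those that appeared later.

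SAP 6.2.4.1 lists "No attributable signs and symptoms present at screening" under NA and takes NA participants out of the denominator of the clinical component rate. For overall response, SAP 6.2.3 and Estimand 2.3 (SAP 2.2.2) have no NA rule: successes are divided by all participants in the population of interest. Those populations are mITT and myITT-IA (SAP 6.2.3) and myITT-IM (SAP 6.3.2).

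**The concern.** The protocol foresees participants with no attributable symptoms at screening, since it gives them their own category, but Table 6 leaves them no way through the clinical column while they remain symptom-free. Clearance of the infection on imaging and mycology does not help. They stay in the denominator, so each one lowers the overall response rate whatever the outcome of treatment.

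It looks like an omission rather than a choice. The SAP component tables treat the clinical and the radiological no-findings-at-screening categories alike: both are NA (SAP 6.2.4.1 and 6.2.4.3). Table 6 treats them differently. It counts the radiological one as met for proven IFD and leaves out the clinical one, without giving a reason.

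Two things are at stake. If Table 6 is applied literally, the rate is pulled down. If some investigators apply it literally and others judge such a participant on the remaining two columns, like cases are classified differently between sites. Data may also be lost: if such a participant were recorded as a failure at an EOT visit before Day 42, Protocol 8.2.8 would waive the Day 42 and Day 84 response assessments.

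**Working it through.** The plan states no figure on this point, so there is none to reproduce. The check is an enumeration of the definition, followed by its effect on the crude rate.

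**Step 1. Count the combinations.** Protocol 8.2.8 offers 5 clinical, 6 radiological and 6 mycological categories, so 5 × 6 × 6 = 180 combinations, of which 6 × 6 = 36 carry the clinical category for no symptoms at screening. Table 6 accepts 2 clinical and 2 mycological categories. It accepts 4 radiological categories at Day 42 and 3 at Day 84, because its footnote withdraws the 25% to 50% band at Day 84.

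| | Day 42 | Day 84 |
|---|---|---|
| Successful combinations, all categories | 2 × 4 × 2 = 16 of 180 | 2 × 3 × 2 = 12 of 180 |
| Successful, no symptoms at screening | 0 of 36 | 0 of 36 |
| Same, if the category met the clinical column | 1 × 4 × 2 = 8 of 36 | 1 × 3 × 2 = 6 of 36 |
| Same, if only documented eradication can apply | 1 × 4 × 1 = 4 of 36 | 1 × 3 × 1 = 3 of 36 |

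The last row matters because presumed eradication, as defined, depends on symptoms resolving. A participant who never had symptoms cannot meet it as written.

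**Step 2. Ceiling on the rate.** Let s be the share of the analysis population recorded in this category and symptom-free throughout. The highest attainable overall response is 1 − s. The documents do not give s. Assumed values of 2%, 5% and 10% give ceilings of about 98%, 95% and 90%.

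**Step 3. Illustration.** Take N = 66, the expected number treated (Protocol 9.5) and so an upper bound for mITT. Assume 7 participants are affected (10% of 66, rounded) and that success would be 60% in both groups. Then 0.60 × 59 ≈ 35 and 0.60 × 7 ≈ 4.

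- Table 6 as written: 35/66 = 53.0% (exact 95% CI 40.3% to 65.4%).
- Category counted as meeting the clinical column: (35 + 4)/66 = 39/66 = 59.1%.
- Category excluded as NA: 35/59 = 59.3%.

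Under these assumptions the literal reading costs about 6 percentage points, well inside the width of the interval.

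**The case against.** The strongest reply is that a reader may infer more than the documents say.

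- *That success is impossible for anyone without symptoms at screening.* Not supported. Clinical resolution and presumed eradication both extend to symptoms that appear at a later visit. Someone who becomes symptomatic and then improves can meet both columns. The gap concerns only those who stay symptom-free.
- *That these participants are failures by definition.* Not supported. Table 6 defines success only. The failure rules name participants who are unavailable, already judged failures, given alternative systemic antifungal therapy, dead, or with an assessment not done. None names this category. The indeterminate outcome is not for them either, since it is reserved for participants without host factors and without proven IFD. The overall response is also the investigator's recorded assessment. For the crude rate the label makes little difference, because a non-success in the full denominator counts the same as a failure.
- *That the mycological column is closed without a repeat invasive test.* Not supported. Mycological assessment is scheduled at Day 42, Day 84 and EOT, and sputum is an accepted specimen (Appendix 9). What stands is that presumed eradication is out of reach as worded, and that documented eradication is defined by an organism cultured or seen at baseline, which leaves a participant diagnosed on GM alone unclear.

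The number affected may well be small. For lower respiratory disease, Appendix 9 separates acute or subacute from chronic infection by onset of symptoms and/or physical findings within about two weeks. Sino-nasal disease needs local pain, ulcer or eschar, or bony extension besides sinusitis. Waiving clinical features for proven IFD says little about symptoms, because for lung and CNS disease those features are imaging signs. This limits the size, but the protocol's own category remains without a place in Table 6.

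It is also fair to say that component and overall denominators differ by general SAP design, since NA is excluded from all three components. That difference alone is not the defect.

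**Conclusion.** The point holds for participants recorded as having no attributable symptoms at screening who remain free of them. As written, Table 6 cannot classify them as overall successes, and the SAP keeps them in the denominator. The direction is downward for mITT, myITT-IA and myITT-IM overall response at EOT, Day 42 and Day 84.

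The size is unknown. The ceilings of about 98%, 95% and 90% rest on assumed shares of 2%, 5% and 10%. The 6-point illustration further assumes that affected participants would respond at the average rate and that Table 6 is applied literally. None of these is an estimate from the documents.

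Overall response is a secondary, descriptive endpoint without hypothesis testing. TEAE incidence and Day 42 all-cause mortality do not use Table 6 and are unaffected. The change is still worth making because the rule gives an evidently unintended result and is easy to amend.

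**What to change.** 1. In the clinical column of Table 6, add a third entry: "No attributable signs and symptoms at screening" and none emerging since. These participants are then judged on the radiological and mycological columns.
2. State the same rule in SAP 6.2.3, so that it also carries to myITT-IM through 6.3.2, and report the number of participants affected in each population.
3. Reconcile the Protocol 8.2.8 definition of presumed eradication for participants who were never symptomatic. How is for the sponsor to decide. Without it, the new entry helps only those with documented eradication.

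The first two items cost one table row, one SAP sentence and a note in the CRF guidance. The third needs a further edit to 8.2.8. The downside is small: the overall response definition changes slightly, and any such participants already assessed need to be reclassified.
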